Informed consent will be obtained before any study procedures are initiated. After providing informed consent, subjects will undergo medical screening (medical history, physical examination, vital signs, urine pregnancy test for women of childbearing potential, psychiatric screening (i.e. Structured Clinical Interview for DSM 5 (SCID) (Dunn et al., 2002), Auditory Hallucination Rating Scale (AHRS) (Hoffman et.al, 2003), Columbia Suicide Severity Scale (C-SSRS) (Posner et al., 2007), Transcranial Magnetic Stimulation Adult Safety Screen (TASS) (Keel et.al., 2001) and audiometry to confirm eligibility. Screening procedures (except for physical exam) may be conducted by an RA trained by the Principal Investigator; consent procedures must be conducted by an MD. A study MD ([name]/PhD) or [name]/PhD) will be available to answer questions, if a subject wishes to speak to a doctor about the risks/benefits of TMS.

Evaluation and motor threshold assessment

Clinical and medical screening includes a physical exam and history, vital signs, review of inclusion and exclusion criteria, and urine pregnancy test (for women). Participants will then have an assessment of resting motor threshold (RMT; 1 minutes). This procedure is described, in detail, below. This session will last about 1 hour.

EEG sessions:

EEG tasks related to AVH will be compared pre/post treatment. There are ~5 hours of EEG recording, which will be done across 2 visits at baseline and post treatment. Each EEG session is expected to last 2.5 hours (1 hour of setup + 1.5 hours of tasks). EEG will be acquired on a 64-channel, active-electrode Brainvision system, digitized at 500 Hz. RAs with EEG data collection experience will conduct this session. All tasks involve listening to sounds via headphones or speakers and some tasks require behavioral responses via button presses or mouse clicks. In some cases subjects are also instructed to view a fixation cross on a monitor or perform a basic visual task while listening to sounds.

MRI (structural MRI, task-related and resting-state functional MRI):

There are ~4 hours of MRI acquisition, which will be done across 2 visits at baseline and post treatment. Each MRI session will include anatomical scans, resting-state fMRI, and an auditory fMRI task. The participant will be placed in a supine position on the table. A head-holder will be used to decrease head movement during the scan. Participants will be given a squeeze ball which

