Transcranial Magnetic Stimulation (TMS) is a noninvasive tool for the study of the human brain that has been approved by the FDA for use in depression and is being investigated as a potential therapeutic agent in other areas of psychiatry and neurology. Contrary to single-pulse TMS, rTMS is able to change and modulate cortical activity that can last beyond the stimulation period, as a potential method for the treatment of neuropsychiatric conditions such as AVHs. We will deliver rTMS at a low frequency (1 Hz) to produce inhibitory effects that may be required to reduce the severity of AVHs. In our protocol, all participants will receive a 20-min once-daily rTMS sessions over a period of 2 weeks (weekends off), and therefore accrue a total of 10 rTMS stimulation sessions. The rTMS parameters that will be used are a frequency of 1 Hz (1 pulse per second) at an intensity of 90% of the motor threshold (MT). Therefore, we will deliver 1200 continuous pulses per session/day which adds up to 12,000 pulses in total for the whole treatment. These parameters are well within established safety guidelines. Although the goal is to deliver 10 sessions over 10 days of rTMS treatment, the treatment will still be considered complete if the participant misses at most two days of treatment over the two week period.

Localization of brain regions for stimulation

Localization of brain regions is done by establishing skull landmarks for each individual and matching these against an MRI of each participant's brain using Brainsight's camera/computer system for coregistration of each participant to his or her MRI. Each individual subject's structural MRI with overlay of the left TPJ target will be used to localize placement of the rTMS coil with frameless stereotaxy (Brainsight, Rouge Research, Inc., Montreal, Canada).

Criteria for Early Discontinuation

Subjects with a Clinical Global Impression-I (CGI-I) worsening of 2 or greater for two consecutive days, or a Clinical Global Impression-S (CGI-S) of 6 or 7 will trigger a clinical evaluation as to whether the patient should be discontinued. This will be documented in the clinical chart. Subjects who are unable to cooperate with study procedures (e.g., TMS, EEG, MRI) will be discontinued from the study.

Blood and other Biological Samples

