These studies entail the recording of EEG from the scalp employing standard sensors and amplification methods. These procedures are well standardized and there are few known risks. These are principally due to equipment malfunction. The recording equipment used in these studies meet the current design criteria for subject safety, including isolation from potential electrical hazards.

MRI

There are no significant risks associated with MRI and fMRI. It is possible that some participants might experience minor distress from the confined and noisy conditions in the scanner. This possibility will be minimized by the use of earplugs, and experienced technicians will monitor all participants for any signs of distress. In the event that a participant becomes anxious during a scan, the study will be halted. Participants will be able to communicate with the investigators at all times using the intercom system should they wish to request that the study be terminated or if they have concerns or questions during the procedure. The participant is in full view of the operator at all times. Participants cannot have an MRI if they have any metallic implants or metal on their person, of if they are pregnant.

The probability of an incidental finding that might lead to the diagnosis of an unknown abnormality is greater than zero. All participants will be alerted to this possibility during the consent process. In that event, participants or their designated physician will be provided copies of their anatomical scans and advised to seek further evaluation if they have concerns.

Measures taken to minimize risks and discomforts related to MRI include: a) a questionnaire used for screening for metallic devices, implants, and other contraindications to scanning; b) exclusion for pregnancy using a pregnancy test prior to scanning; c) exclusion of those unlikely to tolerate the sense of confinement during scanning; d) providing adequate medical, safety monitoring and observation during scanning as appropriate; e) reducing scanning time to that necessary to accomplish the scientific aims of the study; f) enhancing the subjects' physical and emotional comfort during the scan (i.e. ear plugs or headphones for the loud noise produced by the scanner).

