All precautions and protections are given to the participant to ensure that they are as safe and as comfortable as possible. For participants' comfort within the scanner, they lie on a padded table with a pillow to rest their heads on. A blanket is also provided to keep participants warm during the procedure. If the participant appears nervous or anxious, a trained member of the research staff remains with them inside the scanning suite for the duration of the scan. The participant is given a button box to terminate the scan at any time. If he/she pushes the button, he/she will be removed from the scanner immediately. Participants may end the MRI scans at any time.

Methods to Protect Confidentiality

All data (written and electronic) will be coded by number. Personal identifying information will be stored in an electronically secure database at NYSPI. A master list matching subjects with codes will be kept under lock and key, separate from any research records or the computer

database, with access restricted to research staff, to the extent permitted by law. Only staff directly involved in this project will have access to the master list linking subject names to code numbers. All paper records will be kept in a locked office. Computerized data including MRI data will be kept on encrypted computers that are password protected. Any files that contain identifying information will be kept electronically in folders on a computer that is password protected.

In the informed consent form, subjects are told that the information they provide and all findings of testing will be kept strictly confidential, with access limited to the research staff, and possibly state or federal regulatory personnel. All staff members involved in this project are required to receive training in the protection of human subjects. This includes both Good Clinical Practices at Columbia University (entitled Health Sciences: Protection of Human Research Participants [GCP] for Patient-Oriented Clinical Investigators) and the Collaborative Institutional Training Initiative (CITI) at NYSPI.

For remote visits, we will use HIPAA-compliant videoconferencing, phone and web-based platforms.

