De-identified data may also be shared with other investigators at NYSPI for the purposes of substitution in the case of failure of data collection. For instance, if the subject participates in another MRI protocol at NYSPI, and during those sessions the investigators fail to collect all of the needed anatomical and functional MRI sequences, we may share our data with them if we have collected the same types of MRI sequences for our protocol. The inverse may happen as well; we may receive data from another NYSPI protocol if because of a technical failure we are unable to collect all of the necessary MRI sequences.

Direct Benefits to Subjects

Participants may not experience any direct benefits from their involvement in this study.

The proposed project is a clinical trial of TMS for treatment of AVH and an experimental intervention. Therefore, we do not consider AVH treatment a definite benefit of participation. Nevertheless, participants are informed of the purpose of the trial and may in fact experience a reduction in AVH.

MRI findings and clinical assessments are unlikely to be of direct benefit to participants, but subjects will be informed of any clinically significant findings from the MRI and clinical assessments.

Compensation and/or Reimbursement

Subjects will be compensated as follows:

- Pre-treatment session (screening, clinical assessment, EEG and MRI): \$185
- Treatment day: \$100
- Post-treatment session (clinical assessment, EEG and MRI): \$160

In this study, each subject will undergo 1 pre-treatment session, 1 post-treatment session and 10 treatment days. Total compensation for all sessions is \$1345.

Statistical Analysis Plan

We will use a repeated measures t-test to analyze changes in the Auditory Hallucination Rating Scale (AHRS). This involves comparing scores before and after TMS treatment in participants who completed all study procedures. The goal of this analysis is to determine if there are improvements in symptoms of auditory verbal hallucination. Additionally, similar analyses will be performed for secondary outcome measures such as PANSS, investigating if there is a significant decrease in PANSS P3 scores for participants after the TMS treatment sessions.

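### The AHRS t-test is limited to participants who completed every study procedure, which read literally discards valid AHRS pairs; the demonstrable cost is precision, and any bias is of unknown direction

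*Combined protocol and SAP*

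**What the plan says.** The Statistical Analysis Plan specifies a paired t-test on AHRS and gives its analysis set in one sentence: "This involves comparing scores before and after TMS treatment in participants who completed all study procedures". It defines no other analysis set, missing-data rule or sensitivity analysis.

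The procedure table places AHRS at weeks 0 and 3 only. Week 3 also holds audiometry, the other clinical scales, EEG and fMRI. On imaging, the protocol says "There are ~4 hours of MRI acquisition, which will be done across 2 visits at baseline and post treatment"; on EEG, "There are ~5 hours of EEG recording, which will be done across 2 visits at baseline and post treatment". The MRI safeguards add: "Participants may end the MRI scans at any time".

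Two other places bear on completion, and the SAP refers to neither:

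- The rTMS section counts treatment as complete with up to two missed days.
- Criteria for Early Discontinuation removes participants who cannot cooperate with TMS, EEG or MRI. It also says: "Subjects with a Clinical Global Impression-I (CGI-I) worsening of 2 or greater for two consecutive days", or a CGI-S of 6 or 7, "will trigger a clinical evaluation as to whether the patient should be discontinued".

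The documents do not say whether a participant who stops early still has the week-3 AHRS.

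**The concern.** A paired AHRS analysis needs two AHRS scores per person. Making inclusion depend on every other procedure can discard usable outcome data for reasons that have nothing to do with the outcome measure. The set is also undefined at its edge: someone who missed one treatment day, or who ended the second scan early, could be counted in or out. With 10 to 12 people that choice matters, and as written it could be made after the scores are known.

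The AHRS change is the pilot's efficacy signal. The Lay Summary says that promising reductions would lay the ground for a larger sham-controlled trial, so the estimate should rest on all the AHRS data that exist.

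**Working it through.** **Inputs from the documents.** 10 completers required and 12 to be enrolled (Description of Subject Population); AHRS at weeks 0 and 3; paired t-test. **Assumed, because not stated:** two-sided 5% level, normally distributed changes, and at most 12 participants treated.

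**1. The plan's own figure.** 12 − 10 = 2 expected losses, or 2/12 = 16.7%. No alpha, power, effect size or SD is given, so the 10 cannot be reproduced. The two losses need not occur after treatment starts, because full eligibility is assessed only after consent.

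**2. What the test needs against what the rule requires.** The test needs the week-0 and week-3 AHRS. The rule, read literally, also requires week-3 EEG, fMRI and audiometry. Any participant who has the first but not all of the second is an avoidable exclusion.

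**3. Precision.** The 95% CI half-width in SDs of change is t(0.975, n−1)/√n:

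- n = 12: 2.201/3.464 = 0.64
- n = 11: 2.228/3.317 = 0.67
- n = 10: 2.262/3.162 = 0.72

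Ten pairs is what the plan aims for, so 0.72 is not a shortfall against plan. It is the precision given up if 12 pairs exist and two are dropped.

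**4. Bias if exclusion is unrelated to AHRS change.** Bias = (share excluded) × (mean change in those kept − mean change in those excluded). With no difference between the groups this is 0, and the chance of a false finding of improvement stays at 2.5%.

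**5. Bias if exclusion is related to AHRS change (illustration only).** Suppose there is no true change and the lowest m of 12 are lost on a score that correlates ρ with improvement. The expected two lowest of 12 standard normal values are −1.63 and −1.12. The mean among those kept is then

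ρ × 1.63/11 = 0.148ρ for m = 1, and ρ × (1.63 + 1.12)/10 = 0.275ρ for m = 2.

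If instead the most severe are lost, and they would have improved most, the sign reverses. False-improvement rates are from 400,000 simulated null trials per row; repeat runs differ by up to about 0.2 percentage points.

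| Lost | ρ | Losing those who worsened: bias, false improvement | Losing the most severe: bias, false improvement |
|---|---|---|---|
| 1 of 12 | 0.3 | +0.04 SD, 3.5% | −0.04 SD, 1.8% |
| 1 of 12 | 0.5 | +0.07 SD, 4.4% | −0.07 SD, 1.6% |
| 2 of 12 | 0.3 | +0.08 SD, 4.4% | −0.08 SD, 1.5% |
| 2 of 12 | 0.5 | +0.14 SD, 6.4% | −0.14 SD, 1.1% |

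The correlations are assumptions; the documents supply none. The table covers anyone absent from the analysis for any reason. The SAP sentence adds only those who have both AHRS scores and are dropped for something else.

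**The case against.** **The phrase may be loose.** It could simply mean participants who were not discontinued, mirroring the rule on inability to cooperate with TMS, EEG or MRI. That is possible, but the SAP does not say so. It would still leave open a participant who cooperated and then ended one scan early.

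**Imaging failures are partly covered.** Under Methods to Protect Confidentiality, "we may receive data from another NYSPI protocol if because of a technical failure" prevents the collection of MRI sequences. Screening includes "exclusion of those unlikely to tolerate the sense of confinement during scanning", and baseline EEG and MRI should reveal many who cannot tolerate them before any rTMS. This stands as mitigation. It does not cover a refused or aborted week-3 scan, or a missed week-3 EEG. The order of week-3 procedures is not stated, so in some cases no AHRS pair may exist to rescue.

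**The restriction tilts the result towards improvement.** A reader might infer this from the CGI-I trigger and from the foreseen removal for adverse effects. The documents do not support it. Both CGI triggers prompt an evaluation, not automatic removal. CGI is a global rating whose link to AHRS change is unknown. The CGI-S trigger concerns severity, not change, so it could remove the participants with most room to improve. Nothing ties failure of EEG, MRI or audiometry to AHRS change.

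**Changing the analysis set would remove attrition bias.** A reader might infer this too, and it does not follow. Participants discontinued for worsening or adverse effects may have no week-3 AHRS, and any paired t-test omits them.

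**The losses may be few.** The protocol's risk sections cite under 2% stopping TMS for pain and 1 to 5% with psychiatric adverse events. These are not total dropout rates, but 2% of 12 is 0.24 people and 5% is 0.6, below the 1 or 2 modelled. This is also a ten-patient open-label pilot with no stated alpha, so false-positive rates are a secondary yardstick. Both points limit the severity; neither is a reason to discard AHRS pairs.

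**Conclusion.** The point holds as one about the analysis-set wording. Followed literally, the SAP excludes treated participants with valid AHRS pairs for failures the test does not depend on, and its notion of completion is not reconciled with the two other completion rules in the protocol. The cost that can be shown is precision: a half-width of 0.67 to 0.72 SD instead of 0.64 if one or two of 12 pairs are dropped.

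Whether there is bias, in which direction and of what size cannot be settled from the documents. The illustrations span about −0.14 to +0.14 SD, with false improvement from about 1.1% to 6.4% against 2.5%. They rest on assumed correlations of 0.3 to 0.5, one or two losses among 12 treated, no true change and a two-sided 5% test. Even the largest is small beside a half-width of about 0.7 SD.

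Severity is minor to moderate. Confidence is high for the wording only.

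**What to change.** **SAP wording:**

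- Make the main AHRS analysis all participants who received at least one rTMS session and have both a week-0 and a week-3 AHRS, regardless of EEG, MRI or audiometry completion.
- Keep completers as a sensitivity analysis. Define the term, and reconcile it with the two-missed-days allowance and the discontinuation rule for TMS, EEG and MRI.
- Report each loss with its reason and its timing relative to the first rTMS session.

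**One protocol sentence:** state that the scheduled week-3 AHRS is still sought, where the participant agrees, from those who stop early. The analysis-set change alone cannot address bias from people with no post-treatment score.

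**Cost:** the first part needs no new data. The second adds up to about two audiotaped AHRS interviews with second rating, on the planned margin of 12 − 10. The estimated improvement may come out smaller, and some early stoppers may decline, so some missing scores will remain.
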